## ***1 Overview***

### ***1.1 Relevance***

Obesity remains a significant public health problem with the prevalence world wide doubling and now standing at 600 million adults [1]. We are seeing direct rises in obesity related morbidity and mortality, particularly relating to type 2 diabetes, cardiovascular disease and obesity related cancers [2]. Treating Obesity remains a challenging prospect and the role of pharmacotherapies have been limited by their side effects with surgical interventions proving most effective [3]. Bariatric surgery has led the way in terms of effective therapies for obesity with 14-25% reduction in body weight as well as improvement in metabolic risk markers and reduced mortality compared to control groups [4]. Despite the dramatic effects on calorie intake, weight loss and metabolic health, our understanding of mechanisms through which bariatric surgery mediates these effects remains limited. The impact of the altered gut hormone milieu following Roux-en-Y gastric bypass (RYGB) has raised questions regarding the impact of these peptides on food avoidance and food reward patterns. To explore this relationship we will conduct a prospective study objectively measuring food preference and gut peptide responses in patients undergoing RYGB.

## ***2 Study Objectives and Design***

### ***2.1 Objectives***

The primary objectives of this study are

[figure not shown]
1. Determine the effect of Roux-en-Y gastric bypass (RYGB) surgery on food preference using a standardised Buffet meal.
2. Determine if the changes in food preference following RYGB are mediated through changes in gut peptide following surgery.

### ***2.2 Design***

The Study will be conducted in two parts. The first phase of the study is an observational component where participants who are due to undergo RYGB surgery in addition to a matched control group will have their food preference assessed using a standardised macronutrient self selection paradigm (MSSP). This process will be undertaken 1 months pre and 3, 12 and 24 months post surgical intervention (See figure 1). The control group will be studied at matched time points. This will allow determination of the primary outcome, whether RYGB surgery alters food preference. Phase two of the trial will focus on understanding potential mechanisms responsible for altered food preference. It will take the form of a randomised control study whereby subjects following RYGB and controls will be

invited to repeat the MSSP after randomly receiving octreotide or saline placebo in a blinded crossover fashion. This assessment will take place one year following surgery.

**Figure 1: Schematic of Study Design**

**Figure 1.** Each Study visit will include a Buffet lunch, macronutrient self-selection paradigm. Fasting and postprandial blood samples will be collected on all participants. Subjects will be randomised to either 0.9% Saline or Octreotide at the 1 year visit crossing over to the other therapy at their second visit.

### 3 Methodology

#### 3.1 Recruitment

##### 3.1.1 Participants

1. Patients scheduled to undergo bariatric surgery will be recruited from existing clinics.
2. Healthy free-living individuals will be recruited through community and hospital based efforts.

##### 3.1.2 Inclusion/Exclusion Criteria

The inclusion and exclusions criteria for the study are outlined below and in order to participate in the study patients must comply with these criteria.

#### Inclusion Criteria

- Age 18 or over
- Surgical and non-surgical groups:
  - Bariatric surgery
  - Controls with no history of bariatric surgery
- Independently mobile

- Capacity to consent to participate

### **Exclusion Criteria**

- Age <18 years
- Pre-operatively: Factors impairing ability to consume meal
  - Significant dysphagia
  - Gastric outlet obstruction
  - Anything factor that prevents subjects from eating a meal.
- Post-operatively: Factors impairing ability to consume meal
  - Significant and persistent surgical complications or
  - Anything that prevents subjects from eating a meal.
- Systemic or gastrointestinal condition which may affect food intake or preference
- Pregnancy or lactation
- Active and significant psychiatric illness including substance misuse
- Significant cognitive or communication issues
- Medications with documented effect on food intake or food preference
- History of significant food allergy and certain dietary restrictions
- History of liver disease or pancreatitis (Exclusion from Octreotide)
- History of bradyarrhythmia (Exclusion from Octreotide)
- Use of medications with potential serious interactions with Octreotide (Exclusion from Octreotide)

### **3.1.3 Recruitment procedure**

#### **Recruitment of RYGB group**

- Subjects referred to the Bariatric surgery service at St Vincents University Hospital will be considered for recruitment.
- Subjects will be approached after it is confirmed that they are suitable candidates for RYGB. A member of the clinical team will provide potential participants with a letter inviting them to participate in the study.
- Volunteers will be asked to contact the research team if they are interested and a screening visit will be scheduled.
- Written information will be sent to individuals interested in taking part prior to the screening.

- At the study visit the participant will have the opportunity to address any concerns or questions prior to informed consent being obtained.

### **Recruitment of RYGB group (non affiliated)**

Recruitment will be opened up to individuals scheduled to undergo bariatric surgery in centres other than those outlined above. Posters containing information about the study and contact details of the investigators will be distributed to external centres undertaking bariatric surgical procedures. Allowing members of the public undergoing bariatric surgery the opportunity to opt in to the study if they wish.

### **Recruitment of Control group**

Recruitment of the control group will be focused on recruiting healthy free living individuals who did not have bariatric surgery. These subjects will include those recruited by the community and hospital based protocol.

### **Proposed Recruitment methods**

#### **1. Community based campaign**

Posters outlining the study initiative will be placed in public areas including hospital waiting rooms, and universities contact information for the research investigator will be available. Study information will be circulated internally by email at University College Dublin as well as its affiliated hospitals St Vincents University Hospital. Potential participants identified through this method will be able to make contact with the research investigator and they will receive written information detailing the study and be invited to attend a screening visit. If required an open advertisement will be placed in national newspaper.

#### **2. Primary care campaign**

Posters and information sheets relating to the study will be circulated to GP practices in the greater dublin area. We will offer to make a presentation at the UCD and the North Dublin City GP training meetings educating primary care physicians on the ongoing study initiative. GP/GP trainees will be given information supporting this presentation containing contact details for the research investigator that can be given to people identified as potentially suitable in GP practices. Potential subjects identified through this method will be able to make contact with the research investigator, patients will be invited to attend the hospital for a screening visit.

### **3.2 Study Procedures**

#### **3.2.1 Food Preference Questionnaire**

At the screening visit, volunteers will be asked to rate their preferences for 72 different food stuffs using a Likert scale. The items will be categorised into 6 different groups representing depending on their macronutrient content. They will be listed in no particular order. Participants will be asked to rate each individual item along the 9 point scale with the following anchors: 1 = dislike extremely; 5 = neutral; 9 = like extremely. Responses from the Screening Questionnaire will be used to select appropriate foodstuffs for use in a 18 item buffet spread, for each given subject, from the stock list of 72 items. The 18 items selected for the buffet spread will comprise high fat and low fat options combined with varying carbohydrate and protein content.

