### **3.5 Buffet Meal**

The study will take place at the Clinical Research Centre at St Vincents University Hospital. The study methodology will follow the paradigm for food preference assessment developed and validated by Geiselman *et al* [1].

Subjects will be provided with a Food preference questionnaire prior to the study visit. This will ask patients to hedonically/by preference rate each of approximately 90 common foodstuffs of known macronutrient composition on a 9-point Likert scale with the following anchors: 1 = dislike extremely; 5 = neutral; 9 = like extremely. This assessment will be completed by subjects prior to their screening visit, the data sheet will be collected and evaluated by the research investigator. This food preference questionnaire will categorise the 90 food stuffs into each of the 6 cells highlighted in the table below and in no particular order.

Responses from the questionnaire will be used to select appropriate foodstuffs for use in an 18 item buffet spread, for each given subject, from the stock list of 90 items. The 18 items selected for the buffet spread will comprise high fat and low fat options combined with varying carbohydrate and protein content, as depicted in **Table 1**. We will endeavour to provide each subject with foods to which he/she had an intermediate hedonic response (5 – 7). High fat foods given to an individual subject will be paired with a low fat variation of the same food; eg high and low fat meat options, high and low fat cheese options. Stock list foods are all items which are commercially available and require minimal or no preparation (for example slicing fruit, bread or cheese). All food items will be stored and used according to manufacturer’s instructions.

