**Table 1: Macronutrient self-selection paradigm**

	High Simple Sugar	High Complex CHO	Low CHO/High Protein
High Fat	Three foods Fat > 40% Sugar >30%	Three foods Fat >40% Comp Carb >30%	Three foods Fat >40% Protein >13%
Low Fat	Three foods Fat <20% Sugar >30%	Three foods Fat <20% Comp Carb >30%	Three foods Fat <20% Protein >13%

Adapted from Geiselman *et al* [1].

Subjects will be asked to fast from 22:00 the night before the study visit. Subjects may drink water during this period. Volunteers will be asked to abstain from alcohol consumption and strenuous exercise for the preceding 24 hours. Medications may be taken as per usual, but this will be discussed with individual subjects in advance of the study day. Subjects will be asked to come to the CRC at 10:30 on the morning of the assessment. On arrival at the CRF, study documentation and body anthropometry will be completed.

Each subject will have access to their own individual buffet table, in separate rooms, such that subjects cannot observe the selections made by other subjects. Order of foods on the buffet spread will be randomised on each study visit. Containers of known weight of the 12 test foods will be provided to each subject. Subjects will be provided with written and verbal instructions prior to commencing the buffet meal. Volunteers will be instructed that they can now eat their meal and consume as much food as they wish in order to feel “comfortably

full". Patients will be made aware that gut hormone responses will not be optimal if they don't reach a state of being comfortably full, eat the foods they like or if they overeat and feel unwell. Subjects will be reminded that it is important that they understand and follow these instructions, as the blood test for gut hormones will be performed on completion of the meal. They may also eat as much of any particular food type they wish and that it is not a competition. All subjects will be provided with still bottle water to accompany the buffet meal.

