## **9 Statistical analysis**

Data will be analysed using GraphPad Prism (version 6.0) for Windows, GraphPad software (San Diego, CA, USA) and SPSS® (version 20.0) software (SPSS, Chicago, IL, USA). Central tendencies for patient and control group demographics, anthropometric data, caloric intake and macronutrient intake will be calculated and expressed using arithmetic mean  $\pm$  standard error of the mean or median (range), as appropriate. Differences in continuous variables between surgical and control groups will be calculated using the Student's *t* test or Mann-Whitney U test for parametric or non-parametric data, respectively. Correlative analyses will be performed using the Spearman Rho rank correlation to assess the relationship between *ad libitum* caloric intake and macronutrient intake with peri-operative weight loss and anthropometric data. Univariate analysis of factors associated with perioperative and post-surgical weight loss will be performed using Student's *t* test or one-way ANOVA for categorical variables or simple logistic regression for continuous variables. For the multivariate analysis, independent variables which were significant on univariate analysis, including standard demographic, food intake and food preference, will be entered into a multiple logistic regression model with a forward stepwise selection procedure to assess their impact on perioperative and post-surgical weight loss. All statistical analyses will be two-tailed with the threshold of significance set at  $P < 0.05$ .

Although the patients will be tested at all of the time points. Sample size has been estimated based on Gregersen *et al.*[2] who suggest that 35 patients will be required per group in an unpaired study design to detect a 300kJ difference in overall caloric consumption between two groups with a power of 0.8. We anticipate that single-sitting food intake after upper GI surgery will be approximately 60-80% that of matched controls. Given a control *ad libitum* caloric intake of approximately 600kcal, this would equate to a 120 – 240kcal difference in caloric intake. In addition, differences in preferred food types will be studied.

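### Buffet foods are chosen person by person, and section 9 compares intake between RYGB and control using neither the pre-surgery visit nor the composition of the foods offered

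*Combined protocol and SAP*

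**What the plan says.** - **Objective (2.1).** Determine the effect of RYGB on "food preference using a standardised Buffet meal". Section 2.2 makes this the primary outcome and schedules the meal one month before surgery and 3, 12 and 24 months after, with controls seen at matching times.
- **Menu selection (3.2.1, 3.5).** Ratings on a 9-point scale are used to "select appropriate foodstuffs for use in a 18 item buffet spread, for each given subject". Section 3.5 adds that the team will try to "provide each subject with foods to which he/she had an intermediate hedonic response (5 – 7").
- **What is held common (3.5, Table 1).** Everyone gets a 2 x 3 grid with three foods per cell, and "High fat foods given to an individual subject will be paired with a low fat variation of the same food". Cell limits run in one direction only, for example "Three foods Fat > 40% Sugar >30"% against "Three foods Fat <20% Sugar >30"%.
- **Timing (section 4, Table 2; 3.5).** The questionnaire is scheduled at screening only, and the only stated change from visit to visit is the order of the foods. No sentence says that the same foods are served again.
- **Analysis (section 9).** The summary statement is that "caloric intake and macronutrient intake will be calculated and expressed using arithmetic mean" with standard error, or median and range. Surgical and control groups are then compared by t test or Mann-Whitney, two-sided at 0.05. No change from baseline, group-by-time, paired or crossover analysis is named, and intake is not related to what was offered.
- **Controls (2.2, 3.1.3).** They are healthy volunteers without bariatric surgery. They are called matched, but no matching variable is given.

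**The concern.** Someone with no preference, who eats evenly across the table, reproduces the composition of their own menu. Two such people with different menus therefore record different fat and sugar shares. Selection depends on ratings. If one group rates the richest items above 7, the 5-7 rule steers those items off that group's tables, and nothing in the plan makes the ratings of non-randomised groups alike. An average difference in menus between groups would then pass straight into the section 9 comparison and could be read as an effect of RYGB on preference, which is the primary question. This is distinct from the effect of eating less after surgery, because it can arise at equal meal size.

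**Working it through.** **Inputs from the documents:** 35 per group, two-sided 5%, power 0.8 and 300 kJ (section 9); cell limits and 18 foods (Table 1).

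**Assumed:** Table 1 percentages are percent of energy; equal energy is eaten from each food; the between-person SD of percent fat eaten is 8, 10 or 15 points; menu gaps between groups are 2 or 4 points. The documents give none of these.

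**1. The plan's own sample size.** n = 2 × [SD × (1.960 + 0.842) / 300]². Setting n = 35 gives SD = 300 / (√(2/35) × 2.802) = 448 kJ. No SD is stated. SDs of 300, 400, 500 and 600 kJ would give 16, 28, 44 and 63 per group, so 35 can be neither confirmed nor refuted. It is used below only as the group size.

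**2. How far Table 1 lets one person's menu vary.** Requiring sugar or complex carbohydrate above 30% caps fat at 70%; requiring protein above 13% caps it at 87%. Percent fat with no preference:
- lowest: (9 × 40 + 9 × 0)/18 = 20.0%
- highest: (6 × 70 + 3 × 87 + 9 × 20)/18 = 47.8%
- if high-fat foods run 40-60% and low-fat foods 5-20%: (40 + 5)/2 = 22.5% to (60 + 20)/2 = 40%
- if 40-50% and 10-20%: (40 + 10)/2 = 25% to (50 + 20)/2 = 35%

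These are limits for individual menus. They say nothing about group averages.

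**3. What a gap in group-average menus would do.** With gap g and no preference difference, SE = SD × √(2/35) and the noncentrality is g/SE, on 68 degrees of freedom.

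| SD (points) | SE | g = 0 | g = 2 | g = 4 |
|---|---|---|---|---|
| 8 | 1.91 | 5% | 17.8% | 54.1% |
| 10 | 2.39 | 5% | 13.1% | 37.8% |
| 15 | 3.59 | 5% | 8.5% | 19.6% |

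Entries are the chance of p<0.05. A 4-point menu gap corresponds to an 8-point gap in the mean fat content of the nine high-fat foods, since these are half of the menu.

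**4. Calories.** 300 kJ / 4.184 = 72 kcal, which is 72/600 = 12% of the control intake in section 9. At equal weight eaten, a 12% gap in menu energy density would equal the design difference. The plan itself expects a larger drop, 120-240 kcal, so calories are less exposed than macronutrient shares.

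**5. Which comparisons are exposed.** Suppose the menu is fixed and shifts intake by the same g at every visit.
- Group comparison at one post-surgery visit: g remains in full.
- Difference in change from the pre-surgery visit: g − g = 0.
- ANCOVA on baseline intake with slope b: (1 − b) × g remains, because one baseline meal is a noisy measure of the menu's influence. This is why offered composition is worth adding as a covariate.
- Octreotide against saline within a person: g − g = 0.

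The first is the only between-group comparison of intake that section 9 describes.

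**The case against.** The buffet is more standardised than the concern alone suggests. Every participant has nine high-fat and nine low-fat foods, the same three carbohydrate/protein columns, and paired versions of the same food. Only composition within cells can vary. The 5-7 rule is meant to even out liking, and an item that replaces a very rich one must still exceed 40% fat. Section 9 also promises to look at which kinds of food are preferred; if that means share of intake by cell, the outcome is largely immune. The menu appears to be set once before surgery, so a stable offset would largely cancel in within-person change and in the crossover. Finally, menu composition comes from the participant's own ratings, so adjusting a single-visit comparison for it could remove part of a genuine pre-existing preference difference.

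Most of this stands, and it limits the point. It does not remove it. The grid fixes counts and not content, the 5-7 target is only something the team will attempt, and the food-type sentence defines no measure. The within-person comparisons that would give protection are not specified between groups, nor is the reuse of foods stated. The last argument matters less for an effect of surgery: the menu is fixed by pre-surgery ratings, so adjusting for it in an analysis of change does not adjust away something that surgery caused.

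A reader might infer that RYGB and control menus will differ systematically, or that error rates near 54% should be expected. The documents support neither. They contain no ratings or menus by group, and both the gaps and the SDs in the table are posited.

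**Conclusion.** The point holds as a gap in the analysis plan and not as a demonstrated bias. Menus are individual, composition is bounded on one side only, and the planned RYGB-control comparison uses neither the pre-surgery visit nor the foods offered. If average menus differ between groups, that difference enters the result. If they do not, the error rate stays at 5% and individual menus cost only precision. For a 2-point gap the chance of a spurious finding is about 9-18% over SDs of 15 to 8 points. This rests on assumed SDs and gap, on percentages being of energy, and on a comparison at a single visit. It would be going too far to say that the buffet is unstandardised, or that the crossover is affected: the grid and pairing contradict the former, and the latter is protected provided that the same foods are served at both 12-month visits.

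**What to change.** **Section 9.** Make the RYGB-control comparison of each macronutrient share a baseline-adjusted analysis of change from the pre-surgery visit (ANCOVA or mixed model). Add as one covariate the matching composition of that participant's offered menu, for example percent energy from fat over the 18 foods for the fat share, or energy density for calories. Include the covariate at least as a sensitivity analysis. A score defined as deviation from an evenly eaten menu is less suitable, because evenly can mean by weight or by energy.

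**Supporting wording.**
- In sections 3.2.1 and 3.5, state that the foods selected at screening are reused at every visit.
- Tabulate offered composition by group.
- Reconcile the stock list (72 foods in 3.2.1, about 90 in 3.5) and the number served (18 foods, but 12 test foods later in 3.5), since both define what was offered.

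**Cost.** One or two extra covariates per model, one table, and a small calculation from food composition data already held. No stated sample size or other figure changes.

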#### **3.2.2 Participant Information and Consent**

In advance of the study volunteers will have received a copy of the participant information. Any questions and concerns that remain can be discussed with the investigator at the screening visit. If the volunteer meets the inclusion criteria and is satisfied to proceed with recruitment to the study they will be asked to sign the consent form prior to the initiation of any further elements of the study visit. As part of this process every participant will be advised of their right to refuse to participate or to withdraw at any time without impediment to their medical care in accordance with Good Clinical Practice guidelines. Withdrawal from the study can be done at any time by contacting the hospital or research team. If a participant chooses to participate, and subsequently withdraws their consent, all blood samples, records or footage in storage will be destroyed and the information stored will be deleted so it cannot be used again.

